1.7.2 Internal Standard

Identification	Progesterone	H H H
Molecular Formula	C ₂₁ H ₃₀ O ₂	
Lot/Batch Number	SLBQ9723V	
Purity and Expiry	100% - 12 Jan 2019	
Storage Conditions	Room temperature	
Source and Manufacturer	Sigma-Aldrich	
Molecular Weight	314,47 g/mol	
Special Handling Precautions	Usual protection of all personnel conducting the study (mask, gloves and eyeglasses) or According to MSDS (Material Safety Data Sheet)	

1.8 VALIDATION PARAMETERS AND ACCEPTANCE CRITERIA

Data obtained from the entire test will be calculated, in order to verify linearity, precision and accuracy of the method. Table n°1 summarizes the test parameters and acceptance criteria.

Code: GCLP022/01

Page. 9 of 27

Table 1: Test parameters and acceptance criteria for the method validation study

PARAMETERS	TEST	ACCEPTANCE CRITERIA
Selectivity	Analyze 6 different blank AHA samples and compare with the 6 different samples at LLOQ level. ¹	Absence of interfering components is accepted where the response is ≤20% of the LLOQ for the analytes, and ≤ 5% for the IS.
Matrix effect	Verify, for each level of concentration, the matrix factor (MF) for the analytes and for IS Calculate the CV at LQC and HQC of ISnormalized MF using 6 samples in matrix for each level. Verify IS-normalized MF for AHA, for AHA containing Benzalkonium chloride, for AHA containing oxibuprocaine and for AHA containing iodopovidone	Precision (CV)≤ 15%
Linearity	Calculate correlation coefficient (r) and accuracy (%) of back-calculated concentration obtained from 7 non-zero calibration standard defined by LLOQ and ULOQ. Linearity is evaluated on at least three calibration curves.	r≥0.99 Accuracy: ±15% of nominal value (± 20% only at LLOQ) At least 75% of non-zero calibration standard must fulfill this criterion.
Carry-over effect	Analyze one Blank matrix sample injected after ULOQ.	Absence of carry-over effect is accepted where the response is ≤20% of the LLOQ for the analytes, and ≤ 5% for the IS.
LLOQ	Calculate S/N ratio, accuracy and precision by analysis of at least 5 independent LLOQ samples in matrix	S/N ≥5 Accuracy: ±20% Precision (CV) ≤ 20%
Within-run accuracy and precision	Calculate accuracy and precision by analysis of 6 samples per concentration at 4 different concentration extracted from matrix 6 x LLOQ 6 x LQC 6 x MQC 6 x HQC	Accuracy: ±15% of nominal value (± 20% only at LLOQ) Precision (CV) ≤ 15% (≤ 20% only at LLOQ) At least 67% of QCs concentration results should be within 15% of their respective nominal values. At least 50% of QCs at each level should be within 15% of their nominal concentration

¹ Because the aqueous humor is a rare matrix and its collection is difficult (since it is only possible by anterior chamber paracentesis), As deviation from EMA's Guideline on bioanalytical method validation [1], method selectivity will be evaluated on a single batch of artificial aqueous humor (AHA) instead on matrix coming from six different sources.

Code: GCLP022/01

Page. 10 of 27

Table 1 (continue): Test parameters and acceptance criteria for the method validation study

PARAMETERS	TEST	ACCEPTANCE CRITERIA	
Between-run accuracy and precision	Calculate accuracy and precision by analysis of 3 samples per concentration at 4 different concentration extracted from matrix on 5 separated analytical runs, in at least 2 days: 3 x LLOQ 3 x LQC 3 x MQC 3 x HQC	Accuracy: ±15% of nominal value (± 20% only at LLOQ) Precision (CV) ≤ 15% (≤ 20% only at LLOQ) At least 67% of QCs concentration results should be within 15% of their respective nominal values. At least 50% of QCs at each level should be within 15% of their nominal concentration	
Dilution integrity	Calculate accuracy and precision by analysis of 5 independent samples per concentration at two different concentration higher than ULOQ, 5 x > ULOQ 10 times concentrated 5 x > ULOQ 100 times concentrated after 1:10 and 1:100 dilution with blank matrix Analyze these samples against the calibration curve.	Mean Accuracy: ±15% of nominal value Precision (CV) ≤ 15%	
System Suitability Test	Analyze one blank matrix sample. Analyze 1 LLOQ sample.	Absence of interfering compounds (≤20% of the LLOQ for the analytes, and ≤ 5% for the IS). Confirm retention time of analytes and IS. Analytes S/N ≥5.	

Code: GCLP022/01

Page. 11 of 27

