2.3 STANDARD SOLUTIONS

2.3.1 Stock and working standard solutions for calibration sample.

Levofloxacin Stock Standard Solution-1

Weigh accurately about 10 mg of Levofloxacin into a 10 mL volumetric flask, dissolve with methanol then dilute to volume with the same solvent and mix. The concentration of this solution is $2.767 \, \mu mol/mL$.

Code: GCLP022/01

Page. 14 of 27

Dexamethasone 21-phosphate Stock Standard Solution-1

Weigh accurately about 10 mg of Dexamethasone sodium 21-phosphate into a 10 mL volumetric flask, dissolve with water/methanol 50/50 (v/v) then dilute to volume with the same solvent and mix. The concentration of this solution is 1.936 µmol/mL of Dexamethasone 21-phosphate.

Dexamethasone Stock Standard Solution-1

Weigh accurately about 10 mg of Dexamethasone into a 10 mL volumetric flask, dissolve with water/methanol 50/50 (v/v) then dilute to volume with the same solvent and mix. The concentration of his solution is 2.548 µmol/mL.

Intermediate Standard Solution-1a

Transfer 1 mL of Levofloxacin and Dexamethasone Stock Standard Solution-1 into a 10 mL volumetric flask, then dilute to volume with water/methanol 50/50 (v/v) and mix. The concentration of this solution is 0.277 µmol/mL of Levofloxacin and 0.255 µmol/mL dexamethasone.

Intermediate Standard Solution-1b

Transfer 1 mL of Dexamethasone 21-phosphate Stock Standard Solution-1 into a 10 mL volumetric flask, then dilute to volume with water/methanol 50/50 (v/v) and mix. The concentration of this solution is 0.194 µmol/mL dexamethasone 21-phosphate.

Working Standard Solution A

Transfer 1 mL of Intermediate Standard Solution-1a and -1b in a 10 mL volumetric flask, then dilute to volume with water/methanol 50/50 (v/v) and mix.

Working Standard Solution B

Transfer 0.9 mL of Intermediate Standard Solution-1a and -1b in a 10 mL volumetric flask, then dilute to volume with water/methanol 50/50 (v/v) and mix.

Working Standard Solution C

Transfer 0.5 mL of Intermediate Standard Solution-1a and -1b in a 10 mL volumetric flask, then dilute to volume with water/methanol 50/50 (v/v) and mix.

Working Standard Solution D

Transfer 0.1 mL of Intermediate Standard Solution-1a and -1b in a 10 mL volumetric flask, then dilute to volume with water/methanol 50/50 (v/v) and mix.

Working Standard Solution E

Transfer 0.5 mL of Intermediate Standard Solution-1a and -1b in a 100 mL volumetric flask, then dilute to volume with water/methanol 50/50 (v/v) and mix.

Code: GCLP022/01

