Page. 15 of 27

Working Standard Solution F

Transfer 0.1 mL of Intermediate Standard Solution-1a and 0.4 mL of Intermediate Standard Solution -1b in a 100 mL volumetric flask, then dilute to volume with water/methanol 50/50 (v/v) and mix.

Working Standard Solution G

Transfer 0.05 mL of Intermediate Standard Solution-1a and 0.3 mL of Intermediate Standard Solution-1b in a 100 mL volumetric flask, then dilute to volume with water/methanol 50/50 (v/v) and mix.

Store all the solutions at nominally 4°C.

2.3.2 Stock and working standard solutions for QC sample.

Levofloxacin Stock Standard Solution-2

Weigh accurately about 10 mg of Levofloxacin into a 10 mL volumetric flask, dissolve with methanol then dilute to volume with the same solvent and mix. The concentration of this solution is 2.767 µmol/mL.

Dexamethasone 21-phosphate Stock Standard Solution-2

Weigh accurately about 10 mg of Dexamethasone into a 10 mL volumetric flask, dissolve with water/methanol 50/50 (v/v) then dilute to volume with the same solvent and mix. The concentration of his solution is $2.548 \mu mol/mL$.

Dexamethasone Stock Standard Solution-2

Weigh accurately about 10 mg of Dexamethasone into a 10 mL volumetric flask, dissolve with water/methanol 50/50 (v/v) then dilute to volume with the same solvent and mix. The concentration of his solution is $2.548 \mu mol/mL$.

Intermediate Standard Solution-2a

Transfer 1 mL of Levofloxacin and Dexamethasone Stock Standard Solution-2 into a 10 mL volumetric flask, then dilute to volume with water/methanol 50/50 (v/v) and mix. The concentration of this solution is 0.277 µmol/mL of Levofloxacin and 0.255 µmol/mL dexamethasone.

Intermediate Standard Solution-2b

Transfer 1 mL of Dexamethasone 21-phosphate Stock Standard Solution-2 into a 10 mL volumetric flask, then dilute to volume with water/methanol 50/50 (v/v) and mix. The concentration of this solution is 0.194 µmol/mL dexamethasone 21-phosphate.

Code: GCLP022/01

Page. 16 of 27

Working Standard Solution H

Transfer 0.8 mL of Intermediate Standard Solution-2a and -2b in a 10 mL volumetric flask, then dilute to volume with water/methanol 50/50 (v/v) and mix.

Working Standard Solution I

Transfer 1 mL of Working Standard Solution H in a 10 mL volumetric flask, then dilute to volume with water/methanol 50/50 (v/v) and mix.

Working Standard Solution L

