2.4 BIOANALYTICALPROCEDURE

2.4.1 Preparation of calibration standard (CC) and quality control (QC) samples in artificial aqueous humor (AHA)

Use an seven-points calibration curve and three-level of QCs.

Prepare each calibration and QC sample by adding 1 mL of each Working Standard Solution from A to L to 9 mL of artificial aqueous humor (AHA), according to the following scheme:

Code: GCLP022/01

Page. 17 of 27

W	WS concentration (nmol/mL)		AHA concentration (nmol/mL)			ID	SAMPLE	
	Levo	DEX	DEX 21	Levo	DEX	DEX 21		
A	27.672	25.480	19.364	2.767	2.548	1.936	CC A	
В	24.905	22.932	17.428	2.491	2.293	1.743	CC B	
C	13.836	12.740	9.682	1.384	1.274	0.968	CCC	o !!!
D	2.767	2.548	1.936	0.277	0.255	0.194	CC D	Calibration
E	1.384	1.274	0.968	0.138	0.127	0.097	CCE	curve
F	0.277	0.255	0.775	0.028	0.025	0.078	CC F	
G	0.138	0.127	0.581	0.014	0.013	0.058	CC G	
Н	22.138	20.384	15.492	2.214	2.038	1.549	HQC	
I	2.214	2.038	1.549	0.221	0.204	0.155	MQC	QC
L	0.415	0.382	0.871	0.042	0.038	0.087	LQC	

where Levo is levofloxacin, DEX is dexamethasone and DEX 21-P is dexamethasone 21-phosphate

Divide each standard sample in AHA into 20 μ L aliquots, and store at nominally -80°C until analysis. Process calibration curve and QCs samples exactly as described in §2.4.2. Each calibration curve will include a blank sample (AHA sample processed without internal standard) and a zero blank sample (AHA sample processed with internal standard).

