4 METHOD VALIDATION

4.1 SELECTIVITY

Selectivity is the ability to differentiate the analyte of interest and the IS from the endogenous components in the matrix or other component in the sample.

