4.6.1 Procedure

Analyze LQC level (blank matrix spiked with analytes after extraction) in matrix and at the same level (LQC) in absence of matrix (water/methanol 50/50 (v/v)). Repeat the analysis at HQC level. Using the same approach, Matrix effect is also evaluated in order to verify if oxibuprocaine² (use as anesthetic before the surgical procedure), iodopovidone (use as antimicrobial) and benzalkonium chloride (present in the drug product formulation) affect the determination. Oxibuprocaine, iodiopovidone and benzalkonium chloride levels that should be included in aqueous humor in order to define the matrix effect is defined according to literature. Mean values plus 2 times the standard deviation (SD) is tested.

Benzalkonium chloride (BAK) level found in rabbit aqueous humor after 15 drops of 0.05% BAC dosage [3] is $0.52 \pm 0.13 \,\mu\text{g/mL}$: Considering this value as mean \pm Standard Error (worst case) and being the study performed on 24 eyes, SD is 0.637^3 . According to this approach, BAK is tested at 1.8 $\,\mu\text{g/mL}$ in AHA. This is a worst case if compared to drug product posology in clinical study (2 drops of drug product containing 0.1 $\,\text{mg/mL}$ of BAK).

According to literature [4], lidocaine levels in human aqueous humor after administration of 3 and 6 drops of anesthetic at 4 mg/mL are $1.4 \pm 0.5 \,\mu\text{g/mL}$ and $4.2 \pm 1.5 \,\mu\text{g/mL}$ (Mean \pm SD) respectively. Assuming that the same absorption for oxibuprocaine, it is tested at 7.2 $\mu\text{g/mL}$ in AHA, worst case if compared to anesthetic posology (3 drops).

Iodopovidone (0.5% iodine) is used as antimicrobial and is not instilled inside the eye. It is tested at 7.2 μ g/mL in AHA, assuming an absorption similar to oxibuprocaine (worst case).

Prepare WS 1 containing 2.214 nmol/mL of levofloxacine, 2.038 nmol/mL dexamethasone,1.549 nmol/ mL of dexamethasone 21-phosphate and 1.59 nmol/mL of IS in methanol.

Prepare WS 2 containing 0.042 nmol/mL of levofloxacine, 0.038 nmol/mL dexamethasone, 0.087 nmol/ mL of dexamethasone 21-phosphate and 1.59 nmol/mL of IS in methanol.

Prepare LQC and HQC in solvent diluting 20 μ L of WS with 20 μ L of water (use WS1 for HQC and WS2 for LQC)

Prepare LQC and HQC in matrix (use WS1 for HQC and WS2 for LQC):

Matrix 1: 20 μ L of WS with 20 μ L of AHA

Matrix 2: 20 μL of WS with 20 μL of AHA containing BAK 0.8 μg/mL

² Lidocaine may be considered as backup, in case of oxibuprocaine matrix effect.

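### Assay validation never varies levofloxacin against dexamethasone, so some effects of one drug on the other's reading could pass and appear as a difference between arms

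*Combined protocol and SAP*

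**What the plan says.** All section numbers here are from the laboratory protocol (Appendix 12.1) unless marked as the main protocol.

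- **Definition.** Section 4.1 describes selectivity as telling the analyte and internal standard apart "from the endogenous components in the matrix or other component in the sample".
- **Test.** Table 1 in section 1.8 reads: "Analyze 6 different blank AHA samples and compare with the 6 different samples at LLOQ level". Section 4.1.1 likewise sets LLOQ samples against blank artificial aqueous humour.
- **Calibrators.** Section 2.3.1 combines the two drugs at the intermediate step: "Transfer 1 mL of Levofloxacin and Dexamethasone Stock Standard Solution-1 into a 10 mL volumetric flask".
- **Validation QCs.** Section 2.3.2 does the same: "Transfer 1 mL of Levofloxacin and Dexamethasone Stock Standard Solution-2 into a 10 mL volumetric flask". Section 2.4.1 then takes every level from these mixes: "Prepare each calibration and QC sample by adding 1 mL of each Working Standard Solution from A to L".
- **Matrix effect.** Section 4.6.1 uses the same mix: "Prepare WS 1 containing 2.214 nmol/mL of levofloxacine, 2.038 nmol/mL dexamethasone,1.549 nmol/ mL of dexamethasone 21-phosphate", with WS 2 built the same way at the low level. Benzalkonium chloride, oxybuprocaine and povidone-iodine are tested as added substances; levofloxacin is not. Acceptance is on the CV of the normalised matrix factor only.
- **Blinded vials.** Main protocol sections 4.1 and 6.3 add twelve blinded QC vials, four per active substance, without stating their composition, concentrations or limits.
- **No second chance.** Main protocol section 8.2 plans one run without duplicates, and section 10.1.4 has the samples destroyed after analysis.

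**The concern.** Trial samples will not resemble the validation mix. By design the dexamethasone arm has no levofloxacin and the levofloxacin arm has no steroid. The combination product is 5:1 levofloxacin to dexamethasone by strength. Levofloxacin is thus a substance that differs between arms, yet validation never changes its amount relative to dexamethasone. The matrix-effect test cannot show its influence either, because it compares matrix with solvent at identical levofloxacin content, so a levofloxacin effect cancels.

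The main protocol's objective (section 3) sets penetration in combination beside the single products, and section 4.3 adjusts the instilled volume of the dexamethasone product to match dexamethasone content. Readers will put the arm means side by side. A co-drug effect on the reading would follow the randomised arm. With a single unduplicated run and the samples then destroyed, it could not be examined afterwards by re-assay.

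**Working it through.** **1. Reproduce the plan's concentrations.** Inputs: 10 mg in 10 mL stocks, two tenfold dilutions to working solution A, a further tenfold dilution in artificial fluid (sections 2.3 and 2.4.1), and the molecular weights in section 1.7.1 (361.37, 392.46 and 516.41 g/mol). For levofloxacin at level A, 1 mg/mL ÷ 361.37 = 2.767 µmol/mL; after three tenfold dilutions this is 2.767 nmol/mL, or 1000 ng/mL, as tabulated. All 30 table values reproduce to rounding. In ng/mL:

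| Level | Levofloxacin | Dexamethasone | 21-phosphate |
|---|---|---|---|
| A | 1000 | 1000 | 1000 |
| B | 900 | 900 | 900 |
| C | 500 | 500 | 500 |
| D | 100 | 100 | 100 |
| E | 50 | 50 | 50 |
| F | 10 | 10 | 40 |
| G (LLOQ) | 5 | 5 | 30 |
| HQC | 800 | 800 | 800 |
| MQC | 80 | 80 | 80 |
| LQC | 15 | 15 | 45 |

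WS 1 gives 2.214 × 361.37 = 800.1 and 2.038 × 392.46 = 799.8; WS 2 gives 15.2 and 14.9. Levofloxacin and dexamethasone are at equal mass throughout. The 21-phosphate is not, at F, G and LQC.

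This follows the section 2.4.1 table. Read literally, section 2.3.2 prepares the second 21-phosphate stock from dexamethasone, which contradicts that table.

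**2. Additive effect on dexamethasone.** Let the response be x + bL, with x dexamethasone, L levofloxacin and b assumed. In every calibrator and validation QC L = x, so the response is (1 + b)x. The slope absorbs b and back-calculation error is 0% for any b. In patients:

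- dexamethasone arm: x/(1 + b)
- combination arm: (x + bL)/(1 + b)
- ratio of the two at equal true x: 1 + bR, with R = L/x

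The documents give no expected means, so R is an assumption. I use 5 (product strength) and 199.022/15 = 13.3 (ratio of the planning SDs in main protocol section 9.2, not of means).

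| b | R = 5 | R = 13.3 |
|---|---|---|
| 1% | 1.05 | 1.13 |
| 3% | 1.15 | 1.40 |

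**3. Suppression of dexamethasone.** Let levofloxacin at 1000 ng/mL suppress the response by S, under either a linear or a hyperbolic form. A noise-free simulation applied r ≥ 0.99, 75% of calibrators within 15% (20% at LLOQ), LLOQ within 20% and QCs within 15%. Section 4.2.2 leaves linear or quadratic fit and weighting open. Arm ratios assume dexamethasone 30 ng/mL and levofloxacin 150 to 400 ng/mL.

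| Fit | Largest S that passes | Combination/dexamethasone-arm ratio at that S |
|---|---|---|
| Linear, unweighted | about 1% | about 1.00 |
| Linear, 1/x | 15% | 0.93 to 0.98 |
| Linear, 1/x² | 29 to 30% | 0.86 to 0.95 |
| Quadratic | 25 to 52% | 0.68 to 0.95 |

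**4. What the levofloxacin arm would show.** Its apparent dexamethasone is bL/(1 + b). For an assumed L of 200 to 400 ng/mL, b = 3% gives 5.8 to 11.7 ng/mL, above the 5 ng/mL LLOQ; b = 1% gives 2.0 to 4.0 ng/mL, below it.

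**The case against.** The strongest reply is that the trial carries its own control. Every sample is read for all three molecules (main protocol section 8.2), and steroids are barred for seven days before surgery (section 5.2). The levofloxacin arm is therefore about 40 steroid-free samples at trial-level levofloxacin, and additive cross-talk would appear there as dexamethasone in patients who received none. This stands for larger additive effects. It does not expose suppression, and step 4 shows that a 1% effect may stay below the LLOQ. Nor does the plan say these readings will be used this way.

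Several stronger readings are tempting, and the documents do not support them:

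- **That any co-drug effect would pass.** Strong suppression bends the curve and fails the linearity or QC limits. An additive effect on 21-phosphate also fails once b exceeds about 0.7 to 3, depending on the fit, though smaller effects pass.
- **That every QC in the study holds the mix.** The twelve blinded vials may well hold one analyte each, in which case the dexamethasone vials supply the levofloxacin-free condition. Without a stated composition, concentration or limit they cannot be counted on, and single-analyte vials would not mimic a levofloxacin excess.
- **That the product ion at 355.0, common to dexamethasone and 21-phosphate, makes cross-talk likely.** Section 2.2.3 marks both of those transitions for qualitative use. The quantitative ones, 393.2 to 373.1 and 473.1 to 435.1, share no product ion.
- **That cross-talk from 21-phosphate into dexamethasone follows the arm.** Both steroid arms receive 21-phosphate at volumes matched on dexamethasone content, so it is largely common to them.

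The analysis is also purely descriptive, with no hypothesis (main protocol section 9.1). That lowers the stakes, but a biased arm mean is still biased.

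**Conclusion.** The gap is real. Validation holds the levofloxacin-to-dexamethasone ratio fixed at 1:1 by mass and tests selectivity only against drug-free fluid, which falls short of the protocol's own definition. A proportional additive effect on dexamethasone passes at any size, and suppression can pass up to about 1% to 52% depending on the fit.

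This is an untested risk, not a demonstrated interference, and a reader should not infer that the assay is biased. Gradient separation and different precursor masses (362.1, 393.2 and 473.1) make direct cross-talk less likely, and the true effect may be nil. The ratios of 1.05 to 1.13 at b = 1%, and of 0.68 to about 1.00 at the passing limits for suppression, rest on assumed effect sizes and concentrations that the documents do not give.

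**What to change.** Add a co-analyte test to Table 1 and to sections 4.1.1 and 4.6.1, prepared from the separate stocks:

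- **(a) Single analytes.** Read each analyte alone at its ULOQ in the quantitative channels of the others, accepted at the existing limit of 20% of the LLOQ response. For levofloxacin in the dexamethasone channel this allows 0.20 × 5 = 1 ng/mL from 1000 ng/mL, capping b at about 0.1%. The remaining arm ratio is then 1.005 (R = 5) to 1.013 (R = 13.3).
- **(b) With and without.** Test dexamethasone plus 21-phosphate at LQC and MQC, six replicates each, with levofloxacin at 0 and at ULOQ; and levofloxacin at LQC and HQC with and without steroid. Accept on the ratio of the with and without means, within a pre-set limit tighter than ±15%. A range of 0.90 to 1.10 is an example only, for the laboratory to set. Holding each mean within ±15% of nominal is not enough, because it would allow 1.15/0.85 = 1.35 between conditions.

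If the test fails, calibrate levofloxacin and the steroids in separate series before the patient run. State the composition, concentrations and limits of the twelve blinded vials. Report dexamethasone readings in the levofloxacin arm as a cross-talk check. Reconcile the second 21-phosphate stock in section 2.3.2 with the section 2.4.1 table before using it.

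Cost: with six replicates throughout, (b) takes 24 + 24 = 48 injections and (a) takes 18. The total of 66 is 16.5 hours at the 15-minute gradient, plus the calibration curve, blanks and run QCs, and a short laboratory-protocol amendment. It needs no extra patient sample.

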2 MATERIALS, REAGENTS AND METHODS

2.1 MATERIALS AND REAGENTS

2.1.1 Materials

Acetonitrile:

LC/MS grade

Water:

LC/MS grade

Methanol:

HPLC grade

Iso-Propanol:

HPLC grade

Ammonium formiate: for analysis 98-100% Formic acid: for analysis

Sodium chloride: for analysis
Potassium chloride: for analysis
Calcium chloride: for analysis

Sodium hydrogen carbonate: for analysis

glucose: for analysis Urea: for analysis

Albumin: for analysis

Sodium-lactate: for analysis Sodium-ascorbate: for analysis

